### **5.6.1 Discontinuation from Study Treatment Due to Early Non-response to Therapy**

Subjects will be discontinued from study treatment if their early disease response is suboptimal. The Investigator must contact the Medical Monitor to discuss further continuation in the study if the subject meets 1 of the 2 following criteria:

- After 12 weeks of treatment, the subject shows a >30% decrease from baseline value in CKD-EPI eGFR in 2 successive measurements separated by at least 4 weeks

or

- After 8 weeks of treatment, the subject shows a confirmed reduction in UPCR of  $\leq 25\%$  assessed by 2 consecutive measurements at least 2 weeks apart.

If the subjects require treatment with IV methylprednisolone or any rescue medication other than that permitted in the protocol (see Section 7.2.2.2, [Corticosteroids](#)), they should be permanently discontinued from the study treatment and will be considered a treatment failure. Subjects who are permanently discontinued from study treatment will be treated as deemed appropriate by the Investigator.

### **5.6.2 Discontinuation of Study Treatment Due to an Adverse Event**

Subjects may be permanently discontinued from study treatment because of the appearance of an unacceptable AE. It is vital to obtain follow-up data on any subject withdrawn because of an AE. In any case, every effort must be made to evaluate protocol-specified safety follow-up procedures (see Section 10.3, [Reporting Procedure for AEs, SAEs, and Pregnancy](#)). If a subject is withdrawn due to an AE, the event should be followed by the Investigator through contact with the subject until resolution or stabilization has occurred. All AEs should be followed until resolution, stabilization or the subject is lost to follow-up and cannot be contacted.

## **6. RANDOMIZATION, BLINDING AND UNBLINDING PROCEDURES**

### **6.1 Randomization**

All subjects enrolled must be identifiable throughout the study. The Investigator will maintain a list of subject numbers and subject names to enable records to be found at a later date. Subjects will be allocated a subject number at the screening visit and registered with an interactive central randomization system. Subjects meeting the required eligibility criteria will be randomized to treatment at Visit 2 (baseline). The randomization will be stratified by biopsy class (Class V only versus Others) and by prior MMF use at time of screening. The subjects will be randomized in a ratio of 1:1 to receive either Orelvo 23.7 mg BID or matching placebo. To help ensure balance, a centralized randomization will be utilized where region will be employed as a blocked factor.

Details on randomization procedures will be provided in a separate manual.

### **6.2 Blinding**

In order to preserve the double-blind design, subjects randomized to the placebo group will be matched to the active dosage groups. Dosing schedule in the placebo group will be the same as that of the active treatment group. To this end, the double-blind nature of this study preserves the blind with respect to active study treatment and placebo.

All study personnel and subjects will be blinded to the study treatment administered during the study. Orelvo and placebo will be identical in taste, smell, and appearance. The randomization code key will not be available to the Study Monitors, project statisticians or the project team at Aurinia Pharmaceuticals Inc. (Aurinia) or its representatives. The site staff, monitors, and study subjects will remain blinded until the end of the study. In case of emergency, the unblinding process below should be followed.

### **6.3 Unblinding**

In the rare event that an AE or pregnancy occurs for which knowledge of the identity of the study treatment administered is necessary to manage the subject's condition, the IWRS code for that subject may be broken and the test substance identified. Procedures for unblinding will be provided in a separate manual.

Should emergency unblinding be required, the Investigator should call the [REDACTED] [REDACTED] Medical Monitor before unblinding wherever possible; however, the Investigator is responsible for the medical care of the individual study subject, and does not require the agreement of the Medical Monitor before unblinding. The reason for unblinding must be documented. The information on study treatment should only be used for decision

making in the subject's further treatment. Details on unblinded treatment assignments should not be shared with the Study Monitor and project team.

## 7. STUDY TREATMENTS

### 7.1 Dosage Forms/Formulation

All study treatment to be used in this study will be manufactured in accordance with current Good Manufacturing Practice (GMP). Study treatment will be supplied by Aurinia.

#### 7.1.1 Orelvo– Study Treatment

Company Code: [REDACTED]

Chemical Name: [REDACTED]

Empirical Formula: [REDACTED]

Generic Name: Voclosporin

Dosage Form: Softgel capsules

Strength: 7.9 mg of voclosporin per softgel capsule

Manufacturer: [REDACTED]

#### 7.1.2 Placebo Control

Placebo softgel capsules, identical to 7.9 mg Orelvo softgel capsules, will be provided.

#### 7.1.3 Background Therapy

##### 7.1.3.1 Mycophenolate Mofetil

Oral MMF in the form of 500 mg tablets will be centrally supplied by Aurinia. Aurinia will reimburse the cost of the MMF tablets if not centrally provided by Aurinia to the sites.

##### 7.1.3.2 Corticosteroids

Intravenous and oral corticosteroids will be prescribed at the investigational sites and costs will be reimbursed by Aurinia.

## 7.2 Drug Dosage and Administration

### 7.2.1 Treatment Arms

All subjects will receive either 3 capsules of Orelvo (23.7 mg BID) or matching placebo BID.

### **Orelvo – 23.7 mg (3 capsules) BID**

Orelvo 23.7 mg BID; 3 capsules administered BID in combination with MMF and oral corticosteroids from randomization onwards.

### **Placebo – 3 capsules BID**

Placebo; 3 capsules administered BID in combination with MMF and oral corticosteroids from randomization onwards.

## **7.2.2 Dosing Guidelines**

### **7.2.2.1 Orelvo/Placebo – Study Treatment**

Study treatment will be taken BID with water on an empty stomach as close to a 12 hour schedule as possible, and with a minimum of 8 hours between doses. If the subject misses a dose of study treatment by less than 4 hours from the anticipated dosing time, the missed dose will be taken immediately. The next dose will be taken at the originally scheduled time. If a missed dose of study treatment is greater than 4 hours from the expected dosing time, the subject will skip the dose and take the next dose at the originally scheduled time. The variation in dosing will be recorded in the eCRFs. The dose/doses of study treatment may be held at the discretion of the Investigator. Subjects must avoid consumption of grapefruit or grapefruit-containing juice (e.g., pomelo) for the duration of their participation in the study.

**Possible dose adjustments:** If GI or other disturbances occur with study treatment, then study treatment dosing may be reduced or interrupted, and/or appropriate treatment may be initiated (e.g., addition of a proton pump inhibitor (see [Appendix 5](#)) and Section 7.6, [Orelvo/Placebo Dose Modification](#)).

All unused study treatments (and any empty containers) dispensed to the subject will be returned at each study visit for capsule counts to check compliance. The Investigator will count the returned study treatment and this information will be used to assess subject compliance.

This study treatment count must be documented in the eCRF and source documentation.

### **7.2.2.2 Corticosteroids**

All subjects who weigh  $\geq 45$  kg should receive 0.5 g IV methylprednisolone on both Day 1 and Day 2 (a total of 1 g), before oral corticosteroid therapy is started on Day 3. All subjects who weigh  $< 45$  kg should receive 0.25 g IV methylprednisolone on both Day 1 and Day 2 (a total of 0.5 g). When subjects are receiving IV methylprednisolone, they should not receive oral corticosteroids on the same day.

If it is considered to be in the subject's best interest, IV methylprednisolone treatment may be started during the screening period, but no more than 1 g in total may be administered for the

screening period and Day 1 and/or Day 2 combined (0.5 g in subjects who weigh <45 kg). Subjects receiving IV methylprednisolone in the 3 months prior to screening must be discussed with the Medical Monitor prior to initiating further IV methylprednisolone. Also, IV corticosteroid therapy to be administered during screening must be discussed with the Medical Monitor in advance. If IV corticosteroid therapy is administered by the site during screening, the dose administered on Day 1 and/or Day 2 will be 1 g minus the dose administered during screening. The maximum daily dose of methylprednisolone administered on Day 1 and/or Day 2 is 0.5 g. See below for examples:

- Example 1: If a 0.6 g dose of IV methylprednisolone is administered during screening, then  $(1 - 0.6) = 0.4$  g IV methylprednisolone will be administered on Day 1, followed by the oral steroid dosing schedule in [Table 1](#), beginning on Day 2 or 3.
- Example 2: If the dose administered during screening is 0.3 g, then the total residual dose required is  $(1 - 0.3) = 0.7$  g. Because 0.7 g is greater than the maximum daily dose allowed, 0.35 g will be administered on Day 1 and 0.35 g on Day 2, followed by the oral steroid dosing schedule in [Table 1](#), beginning on Day 3. If IV methylprednisolone therapy is administered in the 2 weeks prior to the start of screening then the subject is excluded from the study (see Section 7.8.1, [Prohibited Medications](#)), unless approved by the Medical Monitor.
- Example 3: In a 40 kg subject, if a 0.3 g dose of IV methylprednisolone is administered during screening then  $(0.5 - 0.3) = 0.2$  g IV methylprednisolone will be administered on Day 1, followed by the oral steroid dosing schedule in [Table 1](#), beginning on Day 2 or 3.

If at screening the Investigator determines a subject requires IV corticosteroid therapy, every effort should be made to collect both morning urine specimens (for UPCR determination) before initiation of the IV steroids. If this cannot be done, the Medical Monitor should be contacted in advance of the therapy (see Section 9.2.1, [Screening Visit Procedures](#)).

In the case of the full 1 g IV methylprednisolone being administered prior to randomization (or 0.5 g in a subject <45 kg), it is acceptable for oral prednisone as per dosing schedule to be administered on Day 1.

The starting dose of oral prednisone will be 20 mg/day for subjects <45 kg and 25 mg/day for subjects  $\geq 45$  kg. The dose will be reduced according to the tapering schedule below, see [Table 1](#). Refer to [Appendix 4](#) for a conversion table of various formulations of steroids.

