**Table 1 Dosing Schedule for IV Methylprednisolone and Daily Oral Prednisone (mg)**

	Subjects <45 kg	Subjects ≥45 kg	In Case of Prior IV Steroids During Screening (Pre-randomization)
Weeks 1-2 			
Days 1-2 	0.25 g (IV)	0.5 g (IV)	1 g minus prior IV steroids mg or (0.5 g minus prior IV steroids mg for subjects who weigh <45 kg) 
Days 3-13	20 mg (oral)	25 mg (oral)	
Week 2 (Day 14)	15 mg (oral)	20 mg (oral)	
Week 4 (Day 28)	10 mg (oral)	15 mg (oral)	
Week 6 (Day 42) 	10 mg (oral)	10 mg (oral)	
Week 8 (Day 56)	5 mg (oral)	5 mg (oral)	
Week 12 (Day 84)	5 mg (oral)	5 mg (oral)	
Week 16 (Day 112)	2.5 mg (oral)	2.5 mg (oral)	

1 Day 0-13: Oral steroids dosed according to subject weight and then tapered beginning at Day 14.

2 Oral corticosteroids may be commenced on Days 1 or 2 if corticosteroids are administered during screening.

3 It is recognized that dosing with IV methylprednisolone as described in Section 7.2.2.2, **Corticosteroids** may not be in the subject's best interest if they have already received therapy within the 3 months prior to screening. In this case, the Investigator may be permitted to omit the administration of further IV methylprednisolone but only after discussion with the Medical Monitor.

4 Week 6 is not a scheduled study visit, a phone call can be performed to decide further tapering for subjects.

Notes: Oral prednisone taper should be done within ±3 days of specified timeframe. When clinically indicated, subjects are allowed to be completely titrated off of oral corticosteroids.

Abbreviation: IV = Intravenous.

Note that at each visit or during interim phone calls, the corticosteroid dose to be achieved is shown. The timing of the titration to that dose is at the discretion of the Investigator. For example, the Week 6 administration of steroids in a 43 kg subject should be 10 mg daily. The Investigator may reduce it at Week 7 to 7.5 mg until 5 mg is prescribed at Week 8.

When clinically indicated, subjects are allowed to be completely titrated off of oral corticosteroids.

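### Protocol 7.2.2.2: the rule for the remaining IV methylprednisolone dose omits the <45 kg branch and, read literally, gives those subjects 1.0 g in total instead of 0.5 g (minor)

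*Protocol*

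**What the plan says.** Protocol Section 7.2.2.2 (Corticosteroids) sets the standard IV methylprednisolone course by weight: 0.5 g on each of Days 1 and 2 at 45 kg or more (1 g in total), and 0.25 g on each day below 45 kg (0.5 g in total).

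IV treatment may start during screening. The section then limits the total over the "screening period and Day 1 and/or Day 2 combined (0.5 g in subjects who weigh <45 kg"); at 45 kg or more the limit is 1 g. A few sentences later it gives the rule for what remains to be given after screening use: "the dose administered on Day 1 and/or Day 2 will be 1 g minus the dose administered during screening". The next sentence adds a daily limit, also without a weight split: "The maximum daily dose of methylprednisolone administered on Day 1 and/or Day 2 is 0.5 g".

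Three worked examples follow. Example 2 states no weight and takes a screening dose of 0.3 g: "0.35 g will be administered on Day 1 and 0.35 g on Day 2". Example 3 takes the same screening dose at a lower weight ("In a 40 kg subject, if a 0.3 g dose of IV methylprednisolone is administered during screening then") and arrives at 0.2 g on Day 1.

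Two further places give the low-weight figure. The text on subjects who have had the full dose before randomization treats 0.5 g as the full dose below 45 kg ("or 0.5 g in a subject <45 kg), it is acceptable for oral prednisone as per dosing schedule to be administered on Day 1"), and Table 1 gives the remaining dose as "0.5 g minus prior IV steroids mg for subjects who weigh <45 kg".

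**The concern.** The sentence is an operative dosing instruction. It has no weight branch and does not refer back to the cap. For a subject below 45 kg who received IV steroid at the site during screening, the sentence and the cap cannot both be followed.

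At stake is the dose given to a small subgroup. The protocol deliberately halves the IV steroid dose below 45 kg, and this sentence, applied as worded, undoes that. A site looking for a subject with 0.3 g at screening meets Example 2 first. That example matches the screening dose, carries no weight label, and reaches a total that is wrong for a 40 kg subject.

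**Working it through.** **Inputs, all from Protocol Section 7.2.2.2 and Table 1**

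- Literal rule for Days 1–2: 1 g − s, where s is the screening dose in grams.
- Cap below 45 kg over screening and Days 1–2: 0.5 g, so the remaining dose is 0.5 g − s. Table 1 states the same rule.
- Daily maximum on Day 1 or Day 2: 0.5 g, at any weight.
- Range of s for a subject below 45 kg: above 0 and up to the 0.5 g cap.

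**Step 1. Reproduce the protocol's examples**

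- Example 1: 1 − 0.6 = 0.4 g.
- Example 2: 1 − 0.3 = 0.7 g, split as 0.7 / 2 = 0.35 g per day.
- Example 3 (40 kg): 0.5 − 0.3 = 0.2 g.

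All three match the document. Examples 1 and 2 start from 1 g and Example 3 from 0.5 g, so the examples apply a weight split that the sentence lacks.

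**Step 2. Excess under the literal rule, below 45 kg**

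- Excess on Days 1–2 = (1 − s) − (0.5 − s) = 0.5 g, whatever s is.
- Literal total = s + (1 − s) = 1.0 g.
- Capped total = s + (0.5 − s) = 0.5 g.

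| Screening dose s (g) | Days 1–2, literal (g) | Days 1–2, capped (g) | Excess (g) | Literal dose per day over two days (g) |
|---|---|---|---|---|
| 0.1 | 0.9 | 0.4 | 0.5 | 0.45 |
| 0.3 | 0.7 | 0.2 | 0.5 | 0.35 |
| 0.5 | 0.5 | 0 | 0.5 | 0.25 |

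**Step 3. Does the daily maximum stop the excess?**

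Split over two days, the literal dose is (1 − s) / 2 per day. This is below 0.5 g for every s > 0, as the last column shows. The daily maximum therefore never blocks the literal dose.

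**Step 4. Check the corrected rule**

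With 0.5 g as the starting figure below 45 kg, a 40 kg subject with s = 0.3 g gets 0.5 − 0.3 = 0.2 g and totals 0.5 g. That equals Example 3 and Table 1, so the correction changes no intended dose.

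**The case against.** The strongest reply is that the protocol already resolves the matter. The cap stands in the same paragraph, and the sentence can be read as applying that ceiling, not as permission to exceed it. Example 3 works a low-weight case explicitly, and Example 2, which starts from 1 g, is by implication the case at 45 kg or more. Table 1, the dosing schedule itself, states the weight split. There is also a procedural safeguard: "IV corticosteroid therapy to be administered during screening must be discussed with the Medical Monitor in advance". On this view the excess arises only if someone applies one sentence and ignores everything around it.

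Most of that stands. The intended dose is unambiguous when the section is read as a whole, and the chance of misdosing is low. It does not make the sentence correct: an instruction that states what the dose will be should not need a later example or table to reverse it for a defined subgroup.

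A second objection is that other places also omit the split. Protocol Section 4.1 gives 0.5 g/day for all subjects, and Schedule of Events footnote 20 gives 0.5 g at baseline and Day 2. The observation is accurate, but both concern the standard dose, not the remaining dose after screening use, and both send the reader to Section 7.2.2.2. That is a reason for Section 7.2.2.2 itself to be right.

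**Conclusion.** The sentence is wrong as written for subjects below 45 kg who receive IV methylprednisolone at the site during screening. Followed literally, it gives 1.0 g in total, twice the 0.5 g cap. The excess is 0.5 g at every screening dose from just above 0 to 0.5 g.

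The severity is low. This is an internal inconsistency in one dosing sentence, with the intended rule evident elsewhere in the section. It does not affect the endpoint definition, power, type I error or the analysis. The 0.5 g figure assumes that the sentence is applied without the cap, Example 3 or Table 1. The documents do not say how many subjects weigh less than 45 kg or how many receive IV steroid during screening, so the number who could be affected cannot be estimated.

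**What to change.** In the remaining-dose sentence of Protocol Section 7.2.2.2, insert a parenthetical directly after the 1 g figure giving 0.5 g for subjects who weigh less than 45 kg. The subtraction of the screening dose then applies to the correct starting figure in both weight groups and agrees with the cap, Example 3 and Table 1.

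Nothing else has to change for this rule. If the text is being amended anyway, adding the weight split to Schedule of Events footnote 20 would be sensible tidying, but it is not required because that footnote already refers to Section 7.2.2.2.

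The cost is one parenthetical in the next protocol amendment. It needs no new procedure, data collection or analysis.

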**Table 1 Dosing Schedule for IV Methylprednisolone and Daily Oral Prednisone (mg)**

	Subjects <45 kg	Subjects ≥45 kg	In Case of Prior IV Steroids During Screening (Pre-randomization)
Weeks 1-2 			
Days 1-2 	0.25 g (IV)	0.5 g (IV)	1 g minus prior IV steroids mg or (0.5 g minus prior IV steroids mg for subjects who weigh <45 kg) 
Days 3-13	20 mg (oral)	25 mg (oral)	
Week 2 (Day 14)	15 mg (oral)	20 mg (oral)	
Week 4 (Day 28)	10 mg (oral)	15 mg (oral)	
Week 6 (Day 42) 	10 mg (oral)	10 mg (oral)	
Week 8 (Day 56)	5 mg (oral)	5 mg (oral)	
Week 12 (Day 84)	5 mg (oral)	5 mg (oral)	
Week 16 (Day 112)	2.5 mg (oral)	2.5 mg (oral)	

1 Day 0-13: Oral steroids dosed according to subject weight and then tapered beginning at Day 14.

2 Oral corticosteroids may be commenced on Days 1 or 2 if corticosteroids are administered during screening.

3 It is recognized that dosing with IV methylprednisolone as described in Section 7.2.2.2, **Corticosteroids** may not be in the subject's best interest if they have already received therapy within the 3 months prior to screening. In this case, the Investigator may be permitted to omit the administration of further IV methylprednisolone but only after discussion with the Medical Monitor.

4 Week 6 is not a scheduled study visit, a phone call can be performed to decide further tapering for subjects.

Notes: Oral prednisone taper should be done within ±3 days of specified timeframe. When clinically indicated, subjects are allowed to be completely titrated off of oral corticosteroids.

Abbreviation: IV = Intravenous.

Note that at each visit or during interim phone calls, the corticosteroid dose to be achieved is shown. The timing of the titration to that dose is at the discretion of the Investigator. For example, the Week 6 administration of steroids in a 43 kg subject should be 10 mg daily. The Investigator may reduce it at Week 7 to 7.5 mg until 5 mg is prescribed at Week 8.

When clinically indicated, subjects are allowed to be completely titrated off of oral corticosteroids.

Subjects with a lack of response are allowed one 4-week interval without dose reduction or 1 dose escalation to the previous dose for 2 weeks at any time during the study. Lack of response is defined as no or minimal change in UPCR per Investigator judgment over 3 visits or deterioration in UPCR not meeting the criteria for withdrawal. All deviations from the prescribed dosing schedule in [Table 1](#) above must be discussed with the Medical Monitor and documented in the source notes and eCRF.

### 7.2.2.3 Mycophenolate Mofetil (Background Therapy)

Subjects receiving MMF prior to randomization will continue without interruption.

- Subjects must be counselled on the risk of pregnancy while taking MMF and the need for adequate contraceptive precautions (see Section 5.4, [Adequate/Effective Contraception](#)).
- Subjects on AZA or mycophenolate sodium at screening must switch to MMF at baseline (Day 1).
- For subjects who are not already taking prescribed MMF prior to randomization, the dosing of MMF will start at 500 mg BID for a total daily dose of 1 g/day for the first week, increasing to 1 g BID for a total daily dose of 2 g/day for the second and subsequent weeks (i.e., beginning on Day 8).
- Complete blood count must be performed locally at Weeks 1 and 3 in subjects not already taking MMF at screening (unscheduled visit or not).

All subjects will take MMF BID (morning and evening), before meals (i.e., on an empty stomach), with a glass of water. If a dose is missed, the subject should take the next correct dose rather than “doubling up” at the next dosing time point. A stable dose of MMF will be maintained throughout the study. Dose changes or interruptions are permitted for clearly documented safety reasons only.

- Approval by the Medical Monitor is required for subjects taking a dose other than 2 g/day MMF from randomization onwards (e.g., total daily dose of 1 or 3 g/day).
- If GI disturbance or other side-effects occur with MMF, the 1 g BID dosing may be changed to 500 mg four times daily.
- If a subject has an ANC  $<1,500/\text{mm}^3$  at any study visit, the dose of MMF should be decreased or interrupted. If a subject has an ANC  $<1,000/\text{mm}^3$  at any visit, the dose should be discontinued and only recommenced when the ANC reaches  $1,500/\text{mm}^3$ . If the subject has a dose interruption of MMF of  $>14$  days, then permanent discontinuation of MMF, therefore the study, should be considered after discussion with the Medical Monitor.
- If deemed necessary by the Investigator on account of leukopenia or other adverse effect, or if the subject weighs 50 kg or less, the dose of MMF may be decreased to a minimum of 500 mg BID.

